5.1 Data Relevant to the Primary Outcome

A power analysis was conducted for the primary outcome measure, reduction in time to stone passage. Two published studies^{6,9} provide data on the time from diagnosis to either passage of the kidney stone or complete relief of pain under current standard treatment procedures. Although this time interval varies directly by stone size and location at time of diagnosis, a weighted average of the patient groups in Miller's work⁶ showed an overall mean time interval of about 14 days, and a 30 day passage rate of 90%. In recent Italian studies^{16,46} using tamsulosin and nifedipine in urolithiasis, the overall passage rate of the control arm is much lower. In the control arm of these studies, the 30 day expulsion rate was only 35-43%. We cannot account for this wide variation in overall passage rate between the American and Italian data sets. In order to perform a reliable power analysis, we have used an estimated passage rate of 70% in the placebo group.

As mentioned above in the Background section 2.1.2, in his meta review in 2006, Hollingsworth suggested the need for a definitive clinical study which suggested a sample size very similar to that calculated for our own study.

5.2 Interim Analysis

Interim statistical analyses of clinical trials are a requirement of all National Institutes of Health (NIH) sponsored clinical trials. The Data and Safety Monitoring Committee (DSMC) meets at least once a year to review trial results; however, the exact timing of the interim analyses is at the discretion of the committee. Before each meeting, a formal detailed statistical report will be written by the Biostatistical Coordinating Center (BCC) which presents the results of every aspect of the study, including all baseline variables, protocol adherence, all outcome variables, adverse events reported and center performance in terms of recruitment, data quality, loss to follow-up and protocol violations. However, the main emphasis is on the primary outcome. For this evaluation, a cohort of patients is chosen consisting of all patients randomized before a certain date so that the analysis cohort does not depend on time to stone expulsion.

The main statistical issue relevant to interim analysis is the problem of performing multiple tests of significance on accumulating data. A number of procedures have been developed to handle this situation^{50,51} Most techniques^{52,53} entail adjusting the nominal significance level at the interim evaluations to some value less than α , such that the overall probability of committing a type-I error is maintained at α . For this trial, the group sequential method of Lan and DeMets⁵⁴ will be used to characterize the rate at which the type I error is spent. This method is flexible with regard to the timing of

the interim analyses. Asymmetric stopping boundaries will be used for the Lan-DeMets procedure. The upper boundary which describes the stopping rule for benefit will be based on 1-sided type I error of .025 and the Lan-DeMets generalization of the O'Brien-Fleming boundary. The lower boundary will be based on a less stringent stopping rule: 1-sided type 1 error of .05 and the Lan-DeMets generalization of the Pocock type boundary. However, this should not preclude the Data and Safety Monitoring Committee recommending termination earlier if there is evidence of harm.

Sometimes, a surprising development may lead to extra looks or even continuous monitoring of the data, such as on a monthly basis. The Lan-DeMets procedure is flexible, in that one can switch from occasional to continuous monitoring of the data, with negligible effect on the type I error level.⁵⁵ In some instances the Lan-DeMets boundary for statistical significance may be crossed, but due to other considerations the DSMC decides that the trial should continue. In this case, the type I error previously spent under by the α spending function can be retrieved to be distributed over future looks without inflating the total type I error probability.⁵⁶

It is often useful to calculate conditional power given the observed data to date, and conditional on the future data showing the originally assumed design effect.⁵⁷ If this conditional power is low (under 10 percent) the DSMC may consider termination for futility if the accrual rate is slow with confidence that the Type II error is not greatly inflated.)

It is recognized that any decision to terminate the study would not be reached solely on statistical grounds but on a number of complex clinical and statistical considerations.⁵⁸

5.3 Analysis Plan

5.3.1 Preliminary Analyses

To assess the efficacy of tamsulosin for the treatment of urolithiasis, the BCC will employ a systemic statistical analysis strategy. The first analytic step will be to compile descriptive statistics (e.g. mean, standard deviation, range, proportion) of patient demographics. This activity, while not directly addressing any of the study hypotheses, will serve to describe central tendencies and the variability of outcome variables and co-variables.

Then a series of interactive data analyses will be conducted, which will be used to characterize data distributions, detect any missing data patterns, examine associations and redundancies among independent variables, and generally watch for unusual or unexpected data patterns. This will help verify whether the assumptions of the proposed statistical models are reasonably met and if necessary to choose alternative analytic methods such as non-parametric tests or transformations.

The second step will be to compare treatment groups with respect to important suspected covariates, specifically age, gender, stone location and size, and the number of prior episodes of renal colic. Any variables found to have substantial imbalance (either statistically significant or large in magnitude) between the study groups will be included as covariates. The third step will be to analyze the data according to our specific aims.

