5.3.2 Testing of efficacy and safety outcomes

One of the secondary endpoints is whether the patient requires a more complicated treatment within 90 days of the index emergency visit. This would be evidenced by the need for surgical intervention or lithotripsy. Based on the practice characteristics of the research site we expect a low number of these cases. In addition, work by Yilmaz³⁶ described above lends strong evidence to our expectation that the

surgical intervention rate will be low. These cases will be described descriptively. The two study groups will be compared using the Pearson chi-square test or the Mantel-Haenszel procedure if covariate adjustment is necessary. An additional secondary outcome is the number of days of work missed. These will be tested by t-test or (or ANCOVA with covariates), or if necessary because of distributions requirements, by the Wilcoxon test.

To examine whether the treatment groups experience comparable rates of complications we will monitor patients for several unlikely but potential complications of tamsulosin as outlined above. Events not typically associated with patients with acute urolithiasis will be classified as adverse effects. Adverse and serious adverse events are expected to occur at a very low rate in both study conditions. These will be analyzed descriptively.

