5.5 Statistical Analyses

The principal analyses of primary and secondary outcomes employ the "intent-to-treat" approach as described by Peduzzi.⁶⁰ The intent-to-treat analyses include all randomized patients with all patients included in their randomly assigned treatment group; treatment group assignment is not altered based on the patient's adherence to the assigned treatment regimen. All statistical tests are two-sided with the overall significance level of the primary outcome $\alpha=0.05$. However, the significance levels used in the interim and final analyses of the primary outcome are adjusted to account for the interim analyses.

- *Baseline characteristics:* Comparison of the baseline characteristics (e.g., age, gender, stone location and size) between the two treatment groups uses standard parametric and nonparametric statistical techniques, such as the Pearson chi-square test and Fisher's exact test for categorical data and ANOVA and the Kruskal-Wallis test for continuous data.
- *Primary outcome:* The principal analysis of STONE will be a comparison of the proportion passing stones in the two groups using the Pearson chi-square test. Logistic regression will be used if covariate adjustment is necessary.
- *Secondary outcomes:* Secondary time to event outcomes (e.g., time to passage of stone; time to pain relief) are analyzed using life-table analysis of the time to event. A proportional-hazards regression model is used to evaluate potential covariates that may modify the secondary time to event outcomes (e.g., size and location of stone). Graphical procedures are used to assess the proportionality assumption. If the proportionality assumption is found to be unreasonable, then other models such as the accelerated failure time model or the proportional odds model are used to evaluate the covariates.
- Secondary dichotomous outcomes (e.g., need for surgical intervention or lithotripsy) are analyzed using the same methods as described for the primary outcome. Ordinal outcomes (e.g., number of days lost from work) are analyzed using Poisson regression with adjustment for covariates if necessary. Continuous variables will be analyzed using general linear models.

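### The primary chi-square leaves out site, stone size and stone location; covariates enter only on chance imbalance, and the plan does not say which result is then primary

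*Combined protocol and SAP*

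**What the plan says.** Section 5.5, on the primary outcome: "The principal analysis of STONE will be a comparison of the proportion passing stones in the two groups using the Pearson chi-square test". The next sentence reads: "Logistic regression will be used if covariate adjustment is necessary".

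Section 5.3.1 is the only place that gives that condition a meaning. The groups are compared on five suspected covariates, "specifically age, gender, stone location and size, and the number of prior episodes of renal colic", and then: "Any variables found to have substantial imbalance (either statistically significant or large in magnitude) between the study groups will be included as covariates". No cut-off is given for a large imbalance.

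Section 3.5 and Appendix A stratify randomization by clinical site or center, but no analysis text includes site. Section 2.1 says that stone size and the stone's position affect the likelihood of expulsion. Section 5.1 says that time to passage varies with both. Section 5.5 models them only for secondary time-to-event outcomes and for interactions.

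The same conditional wording reaches the secondary outcomes. Section 5.5 says "Secondary dichotomous outcomes (e.g., need for surgical intervention or lithotripsy) are analyzed using the same methods as described for the primary outcome", and days lost from work "are analyzed using Poisson regression with adjustment for covariates if necessary". Section 5.3.2 says of surgery or lithotripsy: "The two study groups will be compared using the Pearson chi-square test or the Mantel-Haenszel procedure if covariate adjustment is necessary".

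**The concern.** Observed imbalance does not measure how strongly a covariate predicts outcome. Under correct randomization any imbalance is chance, so the rule picks covariates more or less at random. Factors that the protocol itself says drive passage usually stay out of the primary comparison, and the precision they could give is lost.

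The second problem is smaller. Once the rule fires there are two candidate primary results: a difference in proportions from the chi-square comparison and a conditional odds ratio from the logistic model. They estimate different quantities and can fall on opposite sides of 0.05. No text says whether the second replaces or accompanies the first.

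**Working it through.** **1. The plan's sample size.** Inputs from Section 5.4.1: 0.45 versus 0.60, two-sided 0.05, 90% power, 250 per group after losses. With the pooled formula,

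n = [1.960·√(2·0.525·0.475) + 1.2816·√(0.45·0.55 + 0.60·0.40)]² / 0.15² = (1.384 + 0.895)² / 0.0225 ≈ 231 per group.

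250 covers a loss of 1 − 231/250 = 7.6%. The stated figure reproduces.

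**2. How often the rule fires.** Five independent candidates at p<0.05: 1 − 0.95⁵ = 22.6%. Size or location admitted: 1 − 0.95² = 9.75%. With 462 evaluable patients the standard error of a standardized difference is √(4/462) = 0.0930, so p<0.05 corresponds to 0.182. Reading a large imbalance as 0.20 or 0.25 therefore adds nothing; the missing cut-off matters only if it is below 0.182.

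**3. Power.** Simulation, 20,000 replicates per cell, n = 462.

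- From the documents: 0.45 versus 0.60; urn allocation within center (3.5); three centers (7.1); size below 9 mm (3.4.2); 67% of stones below 4 mm (2.1.2).
- Assumed: lognormal size with log-SD 0.44; 65% distal; center split 209/150/150 of 509 (the 109 vanguard patients plus 100 at one center, 150 at each of the others), scaled to 190/136/136; age, sex and prior episodes without effect on outcome.
- Scenario A: size effect linear in mm, no measurement error. Log-odds per mm / location log-odds / site SD: weak −0.2/0.4/0.2, moderate −0.35/0.7/0.3, strong −0.5/1.0/0.4, very strong −0.65/1.3/0.4 (AUC 0.61, 0.68, 0.74, 0.78).
- Scenario B: steps of ±0.4, 0.7 or 1.0 at the size categories of Section 5.3.3, with the same location and site values, 1 mm measurement error, and size fitted as linear.

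The fixed model has treatment, site, size and location, tested by the standardized risk difference. The last column sets size and location to the mean, with a phase indicator, for the vanguard share (99 of 462).

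| Scenario | Chi-square % | Imbalance rule % | Fixed model % | Gain, points | Gain, no vanguard CT data |
|---|---|---|---|---|---|
| A weak | 90.2 | 90.2 | 91.5 | 1.34 | 1.1 |
| A moderate | 90.1 | 90.2 | 92.9 | 2.78 | 2.3 |
| A strong | 90.3 | 90.8 | 94.6 | 4.32 | 3.6 |
| A very strong | 90.2 | 91.1 | 95.9 | 5.67 | 4.8 |
| B weak | 90.0 | 90.0 | 90.8 | 0.84 | 0.8 |
| B moderate | 90.3 | 90.3 | 91.8 | 1.55 | 1.4 |
| B strong | 90.1 | 90.2 | 92.9 | 2.83 | 2.5 |

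The standard error of a gain is 0.10 to 0.18 points. Adjusting for site alone gives 0.2 to 0.7 points. If the covariates are useless there is no material loss (90.0 versus 89.9%). A 220/121/121 split gives nearly the same gains in A (1.29 / 2.79 / 4.43 / 5.81).

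**4. Type I error.** Chi-square 4.7–5.2%; imbalance rule 4.2–5.1%; fixed model 5.1–5.5% with the standardized risk difference, or 4.9–5.2% with the Wald test of the odds ratio, whose gains are 0.2 to 0.3 points lower.

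**5. Two candidate primary results.** The unadjusted design odds ratio is (0.60/0.40)/(0.45/0.55) = 1.83. The conditional odds ratio is 1.88–2.20 in A and 1.86–1.99 in B. When size or location is admitted, weak to very strong, chi-square and logistic disagree at 0.05 in 5 / 9 / 10 / 13% of trials at 45% versus 60%, and in 11 / 18 / 23 / 28% at 45% versus 55%. Over all trials the figures are 0.7–1.5% and 1.5–3.1%.

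**6. Rare secondary outcomes.** At assumed surgery rates of 1 / 2 / 5%, 509 patients give about 5 / 10 / 25 events for five model terms (treatment, two for site, size, location). The chance that some center has no event is 47 / 11 / 0.1%. The primary model should not be carried over to these outcomes.

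**The case against.** The strongest reply is that nothing is invalid: the powered test is the principal test, it holds its size, and extra power beyond a met target is a design preference. That is right about validity, and it is why this point is not a fatal one.

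It can also be said that part of the gain is test size, since the standardized risk difference runs slightly above 5%. Setting each test to its own empirical 5% critical value gave gains of about 0.8 (A weak), 0.3 (B weak) and 0.9 (B moderate) points. So the gain is small where the covariates are weak. But the Wald test holds 4.9–5.2% and loses only 0.2 to 0.3 points of gain, so test size does not explain most of it.

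Replacement is the likelier reading of the logistic sentence, and Section 5.3.2 words the parallel case that way. It is still not stated for the primary outcome. Disagreement between the two results is rare at the design effect.

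Section 2.1 also names a history of spontaneous expulsion. If prior episodes counted as prognostic, the rule would admit some prognostic covariate in 1 − 0.95³ = 14.3% of trials, not 9.75%. That covariate could be added; leaving it out does no harm.

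Baseline comparisons cover all randomized patients, which lowers the 0.182 cut-off to about 0.175 at 500. Section 3.3 names four hospitals and Section 7.1 three centers, so the model needs a definition of site. None of this changes the conclusion.

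**Conclusion.** The concern holds. The primary analysis is valid and adequately powered, but it forgoes precision from data that the trial already collects, and it leaves the primary result unnamed when the imbalance rule fires. The efficiency loss is about 0.8 to 5.7 points of power, 0.8 to 2.8 under the less idealized scenario B; the rule recovers at most about 0.9. Nearly all of the gain comes from size and location, little from site. These figures rest on assumed covariate effects, center sizes and a size distribution; only the direction and the trigger frequencies are free of the assumed effects. The ambiguity affects few trials. The change should be made, but the trial stands without it.

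**What to change.** 1. Section 5.5, primary outcome: specify one logistic model with treatment, clinical site, stone size (continuous, mm) and stone location, reported as a standardized risk difference with 95% CI and p-value. Keep the Pearson chi-square as supportive. Delete "Logistic regression will be used if covariate adjustment is necessary". Define site and the location categories.
2. Section 5.3.1: make the baseline comparison descriptive and remove the imbalance trigger.
3. Section 5.5, secondary dichotomous outcomes: edit the sentence that carries over the primary methods, so that rare outcomes such as surgery or lithotripsy keep the unadjusted chi-square of Section 5.3.2. That section itself says "Based on the practice characteristics of the research site we expect a low number of these cases".
4. For the other secondary analyses in Sections 5.3.2 and 5.5, replace the conditional adjustment with a named covariate set (the same three, or none), since the trigger was its only definition.
5. Use the same primary statistic at interim and final analyses, and write it into the interim procedures that Section 5.5 promises.
6. Confirm that CT size and location exist for the 109 vanguard patients. If not, state the rule for them, for example mean fill plus a phase indicator.

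The sample size stays at 500. The cost is an amendment approved by the Steering Committee and the IRBs (Section 1.3) and a primary estimate that depends on a model, with the chi-square as its check. The coordinating center has already calculated the vanguard placebo passage rate (5.4.1), reports all outcomes to the monitoring committee (5.2), and has its principal investigator on the Steering Committee (7.2.1). The covariates should therefore be fixed by people without access to outcomes by arm. The set proposed here comes from Sections 2.1, 3.5 and 5.1, not from trial data.

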5.3.2 Testing of efficacy and safety outcomes

One of the secondary endpoints is whether the patient requires a more complicated treatment within 90 days of the index emergency visit. This would be evidenced by the need for surgical intervention or lithotripsy. Based on the practice characteristics of the research site we expect a low number of these cases. In addition, work by Yilmaz³⁶ described above lends strong evidence to our expectation that the

surgical intervention rate will be low. These cases will be described descriptively. The two study groups will be compared using the Pearson chi-square test or the Mantel-Haenszel procedure if covariate adjustment is necessary. An additional secondary outcome is the number of days of work missed. These will be tested by t-test or (or ANCOVA with covariates), or if necessary because of distributions requirements, by the Wilcoxon test.

To examine whether the treatment groups experience comparable rates of complications we will monitor patients for several unlikely but potential complications of tamsulosin as outlined above. Events not typically associated with patients with acute urolithiasis will be classified as adverse effects. Adverse and serious adverse events are expected to occur at a very low rate in both study conditions. These will be analyzed descriptively.

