3.3 Design Summary

The multi-center trial will be conducted in the Departments of Emergency Medicine (ED) at The George Washington University Hospital in Washington D.C, Mercy Hospital of Pittsburgh and Presbyterian-University Hospital, both part of the University of Pittsburgh Medical Center, and Thomas Jefferson University Hospital. It is a continuation of the vanguard phase of the study performed solely at The George Washington University Hospital.

This research study is a blinded randomized controlled clinical trial of 400 patients in addition to the 109 enrolled in the vanguard phase. Patients diagnosed with kidney stones via radiographic imaging are approached for screening. Patients who satisfy the eligibility criteria and consent to randomization will be centrally randomized to one of the following two medical protocols, each to be taken once a day for 30 days:

◦ The active group who receive 30 tablets of 0.4 mg tamsulosin.◦ The placebo group who receive 30 similar inactive tablets.
--

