4.5 Patient Management and Follow-up

After randomization, patients are contacted on days 2 and 7, and then on days 15, 20, 29 (to capture status through Day 28), and finally on day 90, as outlined below along with the procedures to be completed in this study and frequency that they will be performed. All the interventions and clinical follow-up in this study are those normally performed in the treatment of patients diagnosed with nephrolithiasis. The only treatment that is not routine is taking tamsulosin or placebo. Follow-up data will be collected in one of three ways: telephone follow-up is the most preferred method, but email communication or texting to the patient's cell-phone can also be used in the case that a telephone call is not feasible.

Table 3: Phone call follow-up Days 2-90

	Day 2	Day 7	Day 15	Day 20	Day 29	Day 90
Study drug taken	X	X	X	X	X	
Total NSAIDs taken	X	X	X	X	X	-
Total Percocet taken	X	X	X	X	X	-
Other analgesics taken?	X	X	X	X	X	-
Stone captured?	X	X	X	X	X	X
Returned to work?	X	X	X	X	X	X
Side effects: Dizzy/nausea/other	X	X	X	X	X	-
Seen PCP for follow-up?	X	X	X	X	X	X
Seen urologist for follow-up?**	X	X	X	X	X	X
Any return ED visits?	X	X	X	X	X	X
Hospitalizations?	X	X	X	X	X	X
Surgical interventions for the stone?	X	X	X	X	X	X
Stone seen on any repeat CT/KUB?	-	-	X	X	X	-
CT scan	-	-	-	-	X	-

**if the patient was seen for urology follow-up, data regarding repeat urinalysis and blood pressure will be collected.

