4.6 Adverse Event Reporting

Detailed information concerning adverse events will be collected and evaluated throughout the conduct of the protocol. Results of clinical observations, laboratory tests, and reported events form the basis for evaluating the safety profile of this therapy. At all contacts, patients will be questioned regarding side effects or symptoms associated with the study medication which are as follows:

- Dizziness at rest
- Dizziness on standing (postural hypotension)
- Abnormal ejaculation (in men)
- Gastrointestinal disorder
- Peptic ulcer disease
- Gastrointestinal bleeding
- Urinary tract infections
- Facial flushing
- Headache
- Tachycardia
- Other side effects

The clinical center will report adverse events to the coordinating center in a timely fashion. The coordinating center will summarize and report adverse events to the DSMB.

Additional procedures are warranted for cases of serious adverse events which is defined by the FDA as a patient outcome that is: (1) death; (2) life-threatening, i.e., the patient was at substantial risk of dying at the time of the adverse event or it is suspected that the use or continued use of the product would result in the patient's death; (3) hospitalization (initial or prolonged); (4) disability, i.e., resulted in a significant, persistent, or permanent change, impairment, damage or disruption in the patient's body function/structure, physical activities or quality of life; (5) congenital anomaly, i.e., there are suspicions that exposure to a medical product prior to conception or during pregnancy resulted in an adverse outcome in the child; (6) requires intervention to prevent permanent impairment or damage. Serious adverse events will be reported immediately to the NIDDK project office, the BCC and the local IRB. The BCC will notify the DSMB chair; and the entire DSMB will confer if needed.

The only indication for breaking the randomization code is when it is medically necessary to unmask the study drug assignment to be able to treat the patient, such as an allergic reaction or severe side effect that appears to be related to the medication.

5 Statistical Considerations

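### Section 5.3.2 can be read to leave stone-like events out of the adverse-effect tables, in conflict with Section 4.6, and Table 3 omits the side-effect question at Day 90

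*Combined protocol and SAP*

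**What the plan says.** Section 5.3.2 treats safety in a few consecutive sentences. The purpose comes first: "To examine whether the treatment groups experience comparable rates of complications", followed by "we will monitor patients for several unlikely but potential complications of tamsulosin as outlined above". Then comes the only classification rule in the plan: "Events not typically associated with patients with acute urolithiasis will be classified as adverse effects". The analysis follows: "Adverse and serious adverse events are expected to occur at a very low rate in both study conditions. These will be analyzed descriptively".

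Section 4.6 makes clinical observations, laboratory tests and reported events the basis of the safety profile, with no exclusion for events that resemble the disease. It says "At all contacts, patients will be questioned regarding side effects or symptoms associated with the study medication" and gives a list that includes gastrointestinal disorder, urinary tract infections and an open category for other side effects. Serious events are defined there by outcome, including hospitalization.

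Table 3 in Section 4.5 has a row "Side effects: Dizzy/nausea/other", marked for Days 2, 7, 15, 20 and 29 and blank (a dash) for Day 90. Section 3.3 describes the study medication as "each to be taken once a day for 30 days".

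**The concern.** Showing that treatment is safe is one of the three goals at the start of Section 5. The rule in Section 5.3.2 sorts events by whether they look like the disease. In a double-blind placebo-controlled trial that sorting is unnecessary, because the placebo arm already carries the disease background and the comparison between arms removes it. Sorting first can only lose information. If events judged typical of stones are left out, an excess of such events on tamsulosin would not appear in the table meant to show it.

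The Day 90 mismatch is a separate matter. If Table 3 governs, there is no side-effect question after Day 29, so the end of the course and the weeks after it are not covered by that question.

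**Working it through.** The plan gives no figure for this point. The check is a comparison of sections, a short piece of algebra and an illustration of size.

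**1. The three events, section by section**

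| Event | Section 4.6 list | Table 3 row, Days 2 to 29 | Called typical of stones anywhere? |
|---|---|---|---|
| Nausea | Not named; could fall under gastrointestinal disorder or other | Named | No |
| Gastrointestinal disorder | Named | Only under other | No |
| Urinary infection | Named | Only under other | No, but linked to the disease |

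On infection, Section 2.1 names ureteral infection as a factor in stone retention, Section 2.2 lists superimposed infection among the complications that lead to admission, and Section 3.4.2 excludes patients with a current infection. An on-study infection could therefore be argued either way under the Section 5.3.2 rule.

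**2. What a filter does, even when applied blind**

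Let p_T and p_C be the true proportions with an event in the tamsulosin and placebo arms, and let a fraction f of those events be set aside as typical of stones, equally in both arms.

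Tabulated difference = (1 − f)p_T − (1 − f)p_C = (1 − f)(p_T − p_C)

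Blinding keeps the filter from favouring an arm, but any excess shrinks by the factor 1 − f. At f = 1 it vanishes.

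**3. Illustration of size**

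Inputs from Section 2.1.1 and Table 1: 1784 patients on 0.4 mg for six months, 811 patient-years, gastrointestinal disorder 18, nausea 17. The planned arm is 250 (Section 5.4.1).

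- Printed percentages: 18/1784 = 1.0% and 17/1784 = 1.0%. Both match Table 1.
- Combined, if no patient is in both rows: 18 + 17 = 35, and 35/1784 = 1.96%.
- Upper figure, with the whole six-month risk falling inside the 30-day course: 0.0196 × 250 = 4.9 patients.
- Lower figure, with a constant rate: 35/811 × 250 × 30/365 = 0.0432 × 20.5 = 0.9 patients.

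Table 1 gives no rate for urinary infection, so none is included.

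**4. Timing of the side-effect question**

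Appendix A has study medication taken for 30 days post-randomization. The last side-effect question is on Day 29, and Section 4.5 says that call is meant to cover status up to Day 28. The uncovered part of treatment is 30 − 29 = 1 day, or 30 − 28 = 2 days if the answers stop at Day 28. After that, 90 − 29 = 61 days pass before the last contact, at which Table 3 does not ask about side effects.

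**The case against.** The strongest reply is that the plan never says stone-like events are excluded. A reader might infer that only atypical events count, but the word only is not in the text. The preceding sentence ties the comparison of rates to complications already outlined. If that means the Section 4.6 list, gastrointestinal disorder and urinary infection are on it. The rule also speaks of adverse effects while the analysis sentence speaks of adverse events, so the rule may be no more than an attribution label. This stands: omission is a possible reading, not a stated rule. It does not settle the matter, because a promise to monitor does not say how an event is counted once judged typical, and nausea is not named in Section 4.6.

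A second reply is that nothing is lost from the database. Table 3 and the follow-up and adverse event forms (Section 6.1) capture the events, serious events are defined by outcome, and repeat ED visits and hospitalizations are secondary outcomes (Section 4.3.2). This also stands, and it limits the concern to the classification and tabulation of non-serious events.

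A third reply concerns Day 90. A reader might infer that nothing is asked after Day 29. Table 3 does not support that: ED visits, hospitalizations, surgical interventions and physician visits are all asked at Day 90. Only the side-effect question is missing.

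Finally, the choice of a descriptive safety analysis is not shown to be wrong.

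**Conclusion.** The point holds as an ambiguity to be removed. Section 5.3.2 contains a classification rule with no definition, no named assessor and no instruction for solicited events judged typical of stones. Read naturally as a definition, it conflicts with the unfiltered basis in Section 4.6. That nausea or gastrointestinal disorder would be judged typical of stones is a clinical assumption which the documents neither state nor rule out.

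The numbers at issue are small: roughly 0.9 to 4.9 patients per 250 on tamsulosin for nausea and gastrointestinal disorder together. A reader might take the upper figure as the expected loss. The documents do not support that, since it places six months of risk inside a 30-day course. The range rests on uncontrolled counts from another population and on no overlap between the two rows. It describes events that could be affected, not a drug excess. In a purely descriptive table of rare events, moving even a few would be visible.

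The conflict over Day 90 between Section 4.6 and Table 3 is plain on the text and minor in size. Both matters merit correction because the remedy costs so little.

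**What to change.** - Replace the classification sentence in Section 5.3.2 with a rule that all solicited and reported events that are new or worsened after randomization are tabulated by arm, whatever their presumed cause.
- If a label for events typical of stone disease is wanted, define its contents in advance, have it assigned blind to treatment, and use it only as an extra breakdown of the full table.
- Reconcile the Section 4.6 list with the Table 3 row, so that nausea and each listed event are asked about and coded the same way.
- Add the side-effect question to the existing Day 90 call, so that Table 3 agrees with Section 4.6.

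The cost is a change of wording, one more question on a call already planned, and longer tables with more background events in both arms.
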